H3c: A higher proportion of post-acute care in the intervention (vs. control) NHs will be enrolled in hospice.

Aim 4: To evaluate the effects of the ACP intervention by comparing outcomes (advance directive orders, hospital transfers, hospice use, and Medicare ACP billing codes) in the intervention vs. control NHs among long-stay residents and newly admitted post-acute care patients who do NOT have designated advanced illness (i.e., dementia, CHF, or COPD).

H4a: A higher proportion of NH patients without advanced dementia, COPD, or CHF in the intervention (vs. control) NHs will acquire advance directives to withhold specific treatments.

H4b: Hospital transfers will be lower among NH patients without advanced dementia, COPD, or CHF in the intervention (vs. control) arms.

H4c: A higher proportion of NH patients without advanced dementia, COPD, or CHF in the intervention (vs. control) NHs will be enrolled in hospice.

Exploratory Aim: Among decedents, to compare the proportion of patients in the intervention and control facilities who had any of the following interventions in the last month of life: hospital transfer or other burdensome interventions (feeding tube insertion, parenteral therapy, intubation, ICU care). Separate analyses will be done among decedents from the short and long-stay cohorts with advanced dementia, CHF or COPD, as well as those without advanced disease.

Cohort and outcomes specifications:

A. Hospital transfer outcome

1. For all analyses involving this outcome, including the primary trial outcome, the main analyses will be restricted to Medicare Fee-for-Service patients because ascertainment of hospital transfers is most accurate from Medicare Claims data. Exploratory analyses will also be done on all patients, not just FFS, using the MDS as well as Medicare claims as the data sources.
2. For the primary outcome and all relevant secondary outcomes, ‘hospitalizations’ was modified to ‘hospital transfers’ based on Medicare claims data, which include admissions, emergency department visits, and observation stays. This change was made so as to capture the main “decision” to send a patient from the nursing home to the hospital.

B. Advance directive outcome

1. For all aims, advance directives analyses will be limited to Genesis facilities in which >75% of patients have any advance directive because the remaining Genesis and Pruitt facilities do not have reliable sources for these data.

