6.1 Data Sources

6.1.1. *Electronic Medical Record (EMR)*. Both NH systems have sophisticated EMR systems in their facilities. Genesis HealthCare uses PointClickCare™,⁹⁸ and PruittHealth uses American Health Tech.⁹⁹ Both EMRs integrate individual patient-level data such as MDS assessments and physician order entry. The EMR will be a source for MDS data, advance directives, and the Video Status Report User Defined Assessment (in intervention facilities only). The EMR will be used to ascertain health care utilization data (i.e., hospital transfers) for patients in Medicare Advantage programs, as Medicare claims will not have these data as they would for patients with traditional fee-for-service Medicare insurance.

6.1.2. *Minimum Data Set Standardized (MDS) Resident Assessment*: The MDS resident assessment instrument has nearly 400 data elements. The assessments are done for all patients admitted to Medicare- and Medicaid-certified NHs, including enrollees in both traditional Medicare and Medicare Advantage. Assessments are done upon admission and at least quarterly thereafter. NHs are required to submit their MDS data to CMS on a regular basis.^{82, 85, 121, 122} Repeated evaluations of the reliability of the MDS yielded adequate to good values on most data items and scales. Brown University investigators found that the “missingness” of elements is low.^{82, 85, 121, 122}

6.1.3. *Medicare Enrollment, Vital Status, and Claims data*: Medicare enrollment and vital status data will be used to obtain death dates and to identify patients enrolled in traditional fee-for-service Medicare or Medicare Advantage insurance programs. Medicare claims ascertain health care utilization data for fee-for-service Medicare beneficiaries, including hospital transfers (hospital admissions, emergency room visits, observation stays, etc.) and hospice enrollment.

6.1.4. *Online Survey Certification Automated Record (OSCAR)*: The OSCAR is a publicly available system of records based upon the Medicare/Medicaid certification and inspection process all NHs being reimbursed undergo. OSCAR data will be used to screen facilities for eligibility (i.e., size) and to describe characteristics of participant NHs (e.g., ownership, size, staffing, services, patient acuity and quality inspection results).^{123, 124}

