9. STATISTICAL CONSIDERATIONS

9.1. General Design Issues

PROVEN is pragmatic cluster RCT of an ACP Video Program intervention for NH patients cared for in two NH health care systems: Genesis HealthCare and PruittHealth. Rationale for this choice of study design is provided in Section 2.6. The intervention will be implemented facility-wide; thus, all patients in the NHs during the 24-month implementation period comprise the study population. However, the analytic plan focuses on the effect of the ACP Video Program vs. control in the following targeted patient sub-groups:

- Long-stay residents (≥ 90 days) with advanced dementia or advanced CHF/COPD (Aim 2)
- Short-stay patients (< 90 days) with advanced dementia or advanced CHF/COPD (Aim 3)
- Long and short-stay patients without these advanced illnesses (Aim 4).

The primary trial outcome is hospital transfers (number of hospital transfers/person-days alive based on Medicare claims data), which include admissions, emergency department visits, and observation stays over a 12-month follow-up period among Medicare fee-for-service long-stay residents with advanced dementia or advanced CHF/COPD. The primary hypothesis is that the rate of hospital transfers will be lower in the intervention group.

Secondary outcomes include hospital transfer rates in the sub-groups examined in Aims 3 and 4, and the following outcomes for all sub-groups in Aims 2, 3 and 4: advance directives, burdensome treatments, hospice use, and Medicare ACP billing codes.

Each long-stay resident will be followed for up to 12 months starting from the date they are first identified as meeting our target cohort definition during the 24-month intervention period and short-stay patients will be followed for 100 days from their NH admission date. The analytic approach to Aims 2, 3, and 4 are similar. Analyses begin with descriptions of all major variables using frequencies and means/medians with SDs/interquartile ranges, as appropriate. Outcomes will be compared between the control and intervention arms using a zero-inflated Poisson model

with random effects to account for clustering at the NH level. While we do not anticipate an effect on mortality, analyses will also examine the effects on mortality. Primary analyses will follow the intention to treat principle and will adjust for minor imbalances in patient characteristics, as needed.

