9.5. Data Analyses

Aim 1: To implement all aspects of a pragmatic cluster RCT: Assessment of Aim 1 will largely be experiential and based on meeting planned recruitment milestones. We will assess the implementation of the ACP Video Program by examining data from the new Video Status Report

User Defined Assessment record created in the EMR that documents the videos offered. Descriptive statistics will be generated describing the proportion of the general NH population and targeted sub-populations exposed to the video, which videos they saw, who saw them (patient and/or family members), who showed the videos (nurse, physician, social worker), and the timing of exposure (i.e., relative to admission, discharge care planning meetings).

Aim 2 To evaluate the effectiveness of the ACP intervention among long-stay NH residents with advanced comorbid conditions: The sample includes long-stay residents with advanced dementia and advanced CHF/COPD. The primary trial outcome is the hospital transfer rate (number transfers/person-days alive based on Medicare claims data), which include admissions, emergency department visits, and observation stays) over a 12-month follow-up period among Medicare fee-for-service) in this cohort. Secondary outcomes include: advance directives (DNR, DNH, DNI, no tube-feeding), burdensome treatments (new feeding tube insertion, intubation, parenteral therapy, ICU care), hospice admission, and Medicare ACP billing codes. All outcomes will be 12-month incidence measures starting from the date residents are first identified as meeting the criteria for definitions of having advanced dementia or CHF/COPD during the 24-month intervention period. While we do not anticipate the ACP intervention to affect mortality,³¹ our analyses will account for censoring during the 12-month observation period. We will formally test for a mortality differential between intervention and controls arms using a logistic regression random effects model, where clustering is performed by facility.

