Using current MDS data from CMS, we observe that the distribution of the primary outcome, hospital transfers, is over-dispersed with many of the patients having no hospital transfer over the 12-month follow up period. In addition, we also observed that hospital transfer rates vary across facilities, even after adjusting for underlying patient risk. To account for these phenomena, we will utilize a zero-inflated Poisson distribution with facility random effects to test and estimate the effects of the ACP intervention. Zero-inflated Poisson models have been used in other public health settings.^{128, 129} Formally, let Y_{ij} be the number of hospital transfers for person i in facility j , N_{ij} is the number of person days alive for person i in facility j , and T_j is a treatment indicator that is equal to one if facility j is in the intervention group. Then where β_1 is the conditional increase in the log hospital transfer rate in facilities that receive treatment vs. those that do not, and α_1 is the conditional log odds ratio for being hospitalized vs. never being hospitalized in the intervention vs. the control arm. When both α_1 and β_1 are smaller than 0, the ACP video is effective in reducing the proportion of patients hospitalized and the number of times hospitalized. Using this model we will estimate the marginal average hospital transfer rate in each arm and calculate the difference between the two arms. We will use a two sided test to examine if the marginal average difference is significantly different than zero, and we will calculate the corresponding interval estimate. As a secondary analysis, we will use the likelihood ratio test to compare the null hypothesis, $H_0 : \alpha_1 = \beta_1 = 0$, to the alternative hypothesis $H_1 : \alpha_1 \neq 0$ or $\beta_1 \neq 0$.¹³⁰ Confidence intervals for α_1 and β_1 can be obtained by inverting the likelihood ratio test.¹³² This analysis will enable us to provide additional details as to whether the effectiveness of the intervention is to reduce the likelihood of one hospital transfer or the number of hospital transfers if transferred at least once.

The secondary outcomes are binary. Commonly used methods applied to the analysis of clustered RCT with binary outcomes are GEE and multilevel models.¹³¹ The former method provides a population “average” effect, while the latter results in a conditional cluster effect. For continuous Gaussian data, interpretation of the treatment coefficient

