$$\begin{aligned}
 p(Y_{ij} = 0) &= \phi_{ij} + (1 - \phi_{ij}) \exp^{-\theta_{ij}} \\
 P(Y_{ij} = y) &= (1 - \phi_{ij}) \frac{\exp^{-\theta_{ij}} \theta_{ij}^y}{y!} \quad y = 1, 2, \dots \\
 \text{logit}(\phi_{ij}) &= \alpha_0 + \alpha_1 T_j + u_j \quad u_j \sim N(0, \sigma_u^2) \\
 \text{log}(\theta_{ij}) &= \beta_0 + \beta_1 T_j + \log(N_{ij}) + v_j \quad v_j \sim N(0, \sigma_v^2)
 \end{aligned}$$

is the same in conditional and marginal models; however, with binary data, the treatment coefficient from a marginal model is smaller than that from a conditional model and has a different interpretation.¹³² For binary outcomes, Bellamy et al¹³³ have shown that with few clusters GEE results were more likely to reject the null hypothesis, while conditional models resulted in more conservative estimates. Austin concluded that the power of GEE and multilevel models are very similar for studies, like ours, that include more than 30 clusters (facilities) with either variable or equal cluster size.¹³⁴ To estimate the effect of ACP on secondary outcomes we will use random effects logistic model. Formally, let S_{ij} one of the secondary outcomes for person i in facility j , and T_j is a treatment indicator that is equal to one if facility j is in the treated arm.

$$\begin{aligned}
 S_{ij} &\sim \text{Ber}(p_{ij}) \\
 \text{logit}(p_{ij}) &= \gamma_0 + \gamma_1 T_j + \zeta_j \\
 \zeta_j &\sim N(0, \sigma_\zeta^2)
 \end{aligned}$$

where γ_1 is the conditional log odds ratio for observing the secondary outcome in the treatment arm vs. the control arm. When γ_1 is smaller than 0, ACP is effective. As for the primary outcome we will use the likelihood ratio test the null hypothesis $H_0 : \gamma_1 = 0$, and by inverting this test we will obtain the corresponding confidence interval.

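### The primary offset counts all days alive, but claims show transfers only while a resident is in fee-for-service Medicare, and no rule ends exposure at exit

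*Combined protocol and SAP*

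**What the plan says.** Numerator: Sections 9.1, 9.4.1 and 9.5 (Aim 2) define the primary outcome as transfers found in Medicare claims over 12 months, per person-day alive.

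Denominator: Section 9.5 says "N_{ij} is the number of person days alive for person i in facility j". It enters the count part of the zero-inflated Poisson model with coefficient 1: "\beta_0 + \beta_1 T_j + \log(N_{ij}) + v_j". The zero part has no exposure term.

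Population: Section 1 (A. Hospital transfer outcome) says "the main analyses will be restricted to Medicare Fee-for-Service patients because ascertainment of hospital transfers is most accurate from Medicare Claims data".

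Limits of claims: Section 6.1.1 turns to the EMR for hospital use by Medicare Advantage patients, "as Medicare claims will not have these data as they would for patients with traditional fee-for-service Medicare insurance".

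Follow-up: Section 9.1 says "Each long-stay resident will be followed for up to 12 months". In a sentence about mortality, Section 9.5 adds that "our analyses will account for censoring during the 12-month observation period", without naming a censoring event or a method.

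Enrolment data: Section 6.1.3 plans to use Medicare enrolment data to "identify patients enrolled in traditional fee-for-service Medicare or Medicare Advantage insurance programs". Table 2 lists insurance only as a covariate, whereas long versus short stay is listed as defining the cohort.

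**The concern.** Numerator and denominator do not cover the same time. Transfers can be seen only while a resident is in fee-for-service. The exposure, as defined, runs until death or 12 months. Restricting to fee-for-service selects people, not days, and the plan does not say whether the status is needed at entry, throughout, or day by day.

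Three primary analyses therefore fit the text: fee-for-service at entry with all days alive counted; continuous fee-for-service required; or exposure ended at exit. The model formula, taken literally, is the first. Under it, a resident who moves to Medicare Advantage contributes days on which no transfer can be recorded. If that resident had no transfer before exit, the zero part of the model can also read them as never transferred. The second analysis selects residents on something that happens after cohort entry. Only the third matches numerator to denominator.

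At stake is the estimate of the marginal rate difference, which is what the two-sided primary test addresses, and the question of which analysis is the pre-specified one.

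**Working it through.** **Inputs from the plan.** Section 9.2 gives a control rate λ0 = 1.51 per person-year, a reduction of 0.25 (so λ1 = 1.26), 90% power, 103 facilities per arm, and 42 target residents per facility. The 42 are not said to be fee-for-service only.

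**Not in the plan, so assumed.** Two-sided alpha 0.05; person-years per facility y; between-facility coefficient of variation k; and the share f of days alive spent outside fee-for-service after cohort entry (range tried: 0 to 20%).

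**The plan's figure.** The cited cluster-rate formula is n = 1 + (z_α/2 + z_β)² [(λ0 + λ1)/y + k²(λ0² + λ1²)] / (λ0 − λ1)². The figure of 103 cannot be reproduced independently because k, y and alpha are not stated. With k = 0 and y = 42, n is about 12. Solving for k at n = 103 gives 0.374 (y = 42) or 0.348 (y = 20). These values are used below only to see how power moves.

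**Equal f in both arms.** The expected observed rate is the true rate × (1 − f).

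- f = 2%: 1.480 vs 1.235, difference 0.245
- f = 5%: 1.434 vs 1.197, difference 0.2375
- f = 10%: 1.359 vs 1.134, difference 0.225
- f = 20%: 1.208 vs 1.008, difference 0.200

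The rate ratio is 1.26/1.51 = 0.834 in every row.

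**Power with equal f.** At 103 per arm and y = 42, power is 90.0% at f = 0, 89.8% at 5%, 89.7% at 10% and 89.2% at 20%. The figures are the same whether all days alive or only observable days are counted, so the small fall is the cost of lost follow-up, not of the denominator. With y = 20, power is 89.3% at f = 10%. With the actual 119 and 241 facilities it stays at about 98.6% for f up to 10% (y = 42).

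**Simulation check.** Settings: 119 and 241 facilities, 42 residents each, k = 0.374, 30% structural zeros, deaths during follow-up, and exits spread evenly over the 12 months. Rates are total transfers over total time, not a fitted zero-inflated model.

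- 10% of residents leave: counting all days alive gives 1.440 vs 1.200, difference 0.240; counting observable days gives 1.509 vs 1.257, difference 0.252. The implied f is 1 − 1.4398/1.5088 = 4.6%.
- 20% leave: counting all days alive gives 1.374 vs 1.146, difference 0.229; counting observable days gives 1.513 vs 1.261, difference 0.252. The implied f is 1 − 1.3743/1.5128 = 9.2%.

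**Unequal f (f0 control, f1 intervention).** The expected difference is 1.51(1 − f0) − 1.26(1 − f1) = 0.25 − (1.51 f0 − 1.26 f1). It is understated only if f1 < (1.51/1.26) f0 = 1.20 f0.

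- f0 = 5%, f1 = 10%: 1.4345 − 1.134 = 0.30, overstated
- f0 = 10%, f1 = 5%: 1.359 − 1.197 = 0.162, understated
- No true effect (1.51 in both arms), f0 = 5%, f1 = 10%: 1.51 × 0.05 = 0.0755, a spurious reduction equal to 30% of the planned effect (0.0755/0.25)

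**The case against.** No sentence says that days after exit will be counted. The fee-for-service restriction could mean continuous enrolment, follow-up is described only as up to 12 months, censoring is to be accounted for, and the definition of N_ij may be no more than model notation. The person-day-alive approach is motivated in Section 9.5 (Aim 3) by high mortality, not by insurance. The size is unknown, because no leaving rate is given. With equal leaving, the rate ratio does not move, power barely moves, and no false effect appears under the null. The plan also has exploratory analyses of all patients using MDS as well as claims.

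Much of this stands. A reader might infer that the plan deliberately counts unobservable days, that the treatment difference will be understated, and that power is lost. The documents support none of the three: the first is a literal reading of a formula, the second needs similar leaving in both arms, and the third is contradicted by the power figures.

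The objection does not remove the mismatch. The written denominator ends only at death or 12 months. The censoring sentence concerns mortality and names no other event. The MDS analyses are exploratory and leave the primary offset as it is.

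**Conclusion.** The point holds as a mismatch in the primary definition with no rule to resolve it; it is not a demonstrated bias. Under the literal reading, and with equal f in both arms, both rates and the absolute difference shrink by (1 − f): a loss of 0.005, 0.0125 or 0.025 from 0.25 at 2%, 5% or 10%. With unequal f, the direction is not determined, and a false difference can arise when there is no effect. That is the stronger reason to settle the rule in advance.

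The result rests on assumed values of f, on transfers after exit being wholly absent from claims, and, for the power figures, on a back-solved k and an alpha of 0.05. The effect on the zero part of the model was not quantified. The point is worth correcting before outcome data are analysed, but it does not undermine the design.

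**What to change.** In Section 9.5, with matching words in Sections 1 and 9.4.1: require fee-for-service enrolment at cohort entry; define N_ij as days alive and enrolled in fee-for-service; censor at the first day outside fee-for-service; and report, by arm, the number of exits and the person-time lost.

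The cost is a few sentences. The enrolment file is already a planned source; this assumes that it dates changes of coverage. The downside is that some follow-up is dropped, and that censoring at exit is taken not to depend on transfer risk. The report of exits by arm gives a partial view of that.

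The offset rule should not be carried over to the hospice, ACP billing and burdensome-treatment outcomes. They are any-event proportions analysed by logistic models without an offset, and burdensome treatments also draw on EMR and MDS. Incomplete fee-for-service follow-up in those outcomes needs its own stated method.

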advanced dementia or advanced CHF/COPD. Outcomes include: advance directives during their NH stay, the number of hospital transfers over 12-months for long-stay or over 100 days for short-stay; and hospice admission over 12 months for long-stay or over 100 days for short-stay. As hospital transfers and hospice enrollment among post-acute care patients are likely to occur after NH discharge, these outcomes can only be assessed among the fee-for-service Medicare beneficiaries using Medicare claims. The outcome, Y_{ij} , is a total count of hospital transfers. Many relatively healthy patients will have $Y_{ij}=0$ while others' hospital use depends on the number of days that they are alive. We will use a zero-inflated Poisson model^{135, 136} of the following form shown in the equation, where $\text{logit}(\pi_{ij}) = X_i\beta + \eta T_i + \delta_{ij}$, X_i are the covariates, η is the treatment effect, and $\varepsilon_{ij} \sim N(0, \sigma_\pi)$ is a random between facility effect. When η is larger than 0 and λ is smaller than 0, ACP video is effective. The same analytic approach described for Aim 2 will be used to evaluate the effectiveness of the intervention.

Sub-Group Analyses of Racial and Ethnic Group Differences in Intervention Effects: It is well-recognized that African-American NH patients with advanced illness are more likely than white patients to have outcomes reflecting more aggressive care, including higher hospitalization rates and lower advance directive documentation rates, even after controlling for patient and facility factors. Nonetheless, there is no evidence suggesting that African American patients respond differently to our ACP intervention than white residents. In fact, the videos have been specifically designed to be appropriate to viewers from all backgrounds

Based on existing data, we anticipate only 11% of the patients included in our analyses will be African-American, and even lower proportions will be of other non-white racial and ethnic groups. Thus, there will not be sufficient power to detect small differences in outcomes among non-white groups. Consequently, these sub-group analyses are necessarily exploratory. Nonetheless, we will conduct sub-group analyses for Aim #2 separately among African-American residents and other racial/ethnic groups (e.g., Hispanic) if numbers allow. Additionally, we will examine differences in video viewing rates among racial and ethnic groups.

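### Section 9.5 reverses the sign rule for α₁ and, for advance directives and hospice, for γ₁; the zero-inflated Poisson coefficients also do not separate any transfer from number of transfers

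*Combined protocol and SAP*

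**What the plan says.** Section 9.5, Aim 2, models transfer counts with a zero-inflated Poisson distribution. A resident is an excess zero with probability φ; otherwise the count is Poisson with mean θ. The linear predictor for logit(φ) is "\alpha_0 + \alpha_1 T_j + u_j", and log(θ) carries β₁ with log person-days alive as offset.

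The text says that α₁ "is the conditional log odds ratio for being hospitalized vs. never being hospitalized in the intervention vs. the control arm", and that when both coefficients "are smaller than 0, the ACP video is effective in reducing the proportion of patients hospitalized and the number of times hospitalized". The coefficient-level analysis is secondary. It is meant to show whether the intervention works "to reduce the likelihood of one hospital transfer or the number of hospital transfers if transferred at least once". The primary inference is separate: "We will use a two sided test to examine if the marginal average difference is significantly different than zero".

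For Aim 4, the treatment coefficient η sits in logit(π), where π is again the excess-zero probability. The rule there is: "When η is larger than 0 and λ is smaller than 0, ACP video is effective".

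For binary secondary outcomes, Section 9.5 defines γ₁ as the log odds ratio of the outcome occurring, treated versus control. It reads a negative γ₁ as effective and makes no exception by outcome.

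**The concern.** A prespecified rule for reading coefficients should settle direction before results are seen. Here there are three faults.

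1. The α₁ definition and rule contradict the equation that contains α₁, and contradict the Aim 4 rule.
2. The γ₁ rule would count fewer advance directives and less hospice use as success, although H2a, H2c, H3a, H3c, H4a and H4c predict more.
3. The promised split between any transfer and number of transfers cannot be read from α₁ and β₁.

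At stake is the written conclusion of the secondary mechanism analysis and of the directive and hospice outcomes.

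**Working it through.** **α₁.** From the printed model:

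- P(Y=0) = φ + (1-φ)exp(-θ), so a larger φ means more residents with no transfer.
- logit(φ) contains α₁T, so α₁ > 0 raises φ in the intervention arm. The favourable sign is α₁ > 0.
- The text takes α₁ as hospitalized versus never, and calls α₁ < 0 favourable. This is reversed. The Aim 4 rule (η > 0) agrees with the equation. The β₁ < 0 half of the Aim 2 rule is right.

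**What the misreading could do.**

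- From Section 9.2: control rate 1.51 per year and a reduction of 0.25, giving 1.26. Placed wholly on θ, this is β₁ = ln(1.26/1.51) = -0.181.
- Assumed: φ from 0.1 to 0.5 and the values of α₁ (neither is in the documents), random effects at zero, and one full year alive unless stated.
- Control θ = 1.51/(1-φ). Intervention: φ′ = expit(logit φ + α₁), θ′ = θ·exp(β₁).
- P(Y≥1) = (1-φ)(1-exp(-θ)).

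Worked example, φ = 0.3, α₁ = -0.5, β₁ = -0.1: θ = 1.51/0.7 = 2.157, and control P(Y≥1) = 0.7 × (1-exp(-2.157)) = 61.9%. Intervention φ′ = 0.206 and θ′ = 1.952, so P(Y≥1) = 0.794 × (1-exp(-1.952)) = 68.1%.

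In (a) to (c) both coefficients are negative, so the Aim 2 rule reports a reduced proportion hospitalized in every cell. P(any transfer):

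| φ | Control | (a) α₁ -0.5, β₁ -0.1 | (b) α₁ -0.3, β₁ -0.181 | (c) α₁ -0.1, β₁ -0.181 |
|---|---|---|---|---|
| 0.1 | 73.2% | 73.2% | 69.6% | 68.5% |
| 0.2 | 67.9% | 71.1% | 66.9% | 64.7% |
| 0.3 | 61.9% | 68.1% | 63.4% | 60.1% |
| 0.4 | 55.2% | 63.9% | 58.7% | 54.7% |
| 0.5 | 47.6% | 58.2% | 52.8% | 48.3% |

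The reported reduction is wrong in (a) throughout (unchanged to one decimal at φ = 0.1, higher above), in (b) from φ = 0.3, and in (c) only at φ = 0.5.

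Break-even α₁ at β₁ = -0.181, below which the proportion rises:

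| Time alive | φ 0.1 | 0.2 | 0.3 | 0.4 | 0.5 |
|---|---|---|---|---|---|
| 1 year | -1.33 | -0.40 | -0.21 | -0.12 | -0.07 |
| 0.5 year | none | -0.77 | -0.41 | -0.26 | -0.18 |

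At half a year and φ = 0.1 the proportion always falls.

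**Separation.** E(Y|Y≥1) = θ/(1-exp(-θ)) depends on θ only, but P(Y≥1) depends on φ and θ. With α₁ = 0 and the whole 1.51 to 1.26 effect on θ:

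| φ | P(any), control to intervention | E(Y given Y≥1) |
|---|---|---|
| 0.1 | 73.2 to 67.8% | 2.06 to 1.86 |
| 0.3 | 61.9 to 58.4% | 2.44 to 2.16 |
| 0.5 | 47.6 to 46.0% | 3.17 to 2.74 |

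Both quantities fall although α₁ is zero. Someone reading the coefficients would conclude that the likelihood of a transfer had not changed.

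**γ₁.** Section 1 (parts B and D) codes the event as having a directive (DNR, DNH, DNI or feeding restriction) or a hospice claim. The hypotheses predict higher proportions, so benefit is γ₁ > 0. For scale, using the 2007 DNH and no-tube-feeding prevalences in Section 2.2 (4% and 11%), an illustrative γ₁ = -0.3 lowers them to 3.0% and 8.4%, which the rule calls effective. The rule is right for burdensome interventions (H2b). For Medicare ACP billing the documents state no direction.

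**The case against.** Nothing that decides the trial changes. The primary test is two-sided on the marginal rate difference, and the likelihood ratio tests are non-directional. The intended directions are plain elsewhere, for example in Section 9.1: "The primary hypothesis is that the rate of hospital transfers will be lower in the intervention group". An analyst would have to ignore six written hypotheses to call fewer directives a success. This stands, and it keeps the point minor.

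The numerical examples rest on assumed φ and coefficients. In case (a) at φ of 0.3 to 0.5 the marginal rate also rises (1.51 to between 1.55 and 1.70), so the primary estimate would expose the misreading. That is true of those cells. It is not true of case (b) at φ = 0.3, where the marginal rate falls to 1.37 while the proportion transferred rises from 61.9% to 63.4%.

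On separation, the plan does not say that α₁ alone gives P(Y≥1); never hospitalized could mean the latent excess-zero class; and E(Y|Y≥1) is indeed free of α₁. That half of the split largely holds. But the plan promises information on the likelihood of a transfer, which the excess-zero coefficient alone does not supply even with its sign corrected.

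Finally, the γ₁ rule is printed under Aim 2. It reaches H3 and H4 because Section 9.1 calls the approach for Aims 2 to 4 similar and the Aim 4 text adopts the Aim 2 approach.

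**Conclusion.** The concern holds, as a minor point. The α₁ and γ₁ conflicts follow from the printed text and need no assumptions. The separation point follows from the algebra of the model. The primary test, likelihood ratio p-values, intervals and sample size are untouched. The risk is a wrong written conclusion: under the Aim 2 rule, a smaller proportion hospitalized could be claimed when that proportion is unchanged or higher, and a favourable result (α₁ > 0, β₁ < 0) would fail the rule. How often this would occur cannot be said, because φ and the division of the effect between the two model parts are not in the documents. At the planned effect on θ with a full year alive, it requires α₁ below -1.33 at φ = 0.1, but only below -0.07 at φ = 0.5.

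**What to change.** - Define α₁ as the log odds ratio of being an excess zero, with benefit at α₁ > 0 and β₁ < 0. Alternatively, model logit(1-φ) and keep the present text. Use one convention for Aims 2 and 4.
- Answer the mechanism question with P(Y≥1) and E(Y|Y≥1) by arm, with intervals, from the fitted model.
- State benefit as γ₁ > 0 for advance directives and hospice and γ₁ < 0 for burdensome interventions. For ACP billing, state a direction or say that none is prespecified.

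The cost is SAP wording and two quantities derived from a model already being fitted. Data, tests and sample size do not change.
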